## 6.2.3 Rescue medication

There will be no rescue medication for nAMD in the study eye.

In case of lack of efficacy with the investigational drug for nAMD and if the investigator deems it is in the best interest of the patient to receive prohibited treatment ([Section 6.2.2](#)) in the study eye, the investigator should follow the instructions for study treatment discontinuation or study discontinuation provided in [Section 9](#).

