### q12w/q8w treatment phase

The mandatory visit at Week 12 will be performed to evaluate the primary endpoint of the study. No treatment will be administered at Week 12; the next visit will take place at Week 16. Disease activity will be assessed at Week 12 for endpoint assessment purposes.

The q12w/q8w treatment phase starts at Week 16 and is defined as follows:

- Following Week 8, treatment intervals will be either 8 weeks or 12 weeks. A patient must be discontinued from further study treatment if treatment is required more frequently, i.e., every 4 weeks.
- The first assessment of disease activity during this phase will be performed at the Week 16 visit by the investigator.
- Based on investigator's judgment of visual and/or anatomic outcomes, the treatment can be adjusted by the investigator to a q8w treatment regimen if there is disease activity as

provided in the guidance to the investigators, e.g. decrease of visual acuity and/or other signs of the disease (e.g. IRF, SRF, sub-RPE fluid, retinal hemorrhage, CRT increase, etc.).

- The disease activity assessment is performed at each subsequent visit by the investigator.
- If disease activity is identified, the patient will be reassigned to receive injections q8w thereafter up to Week 40/Week 44.
- Regardless of treatment administration, Week 16 and Week 48 visits are mandatory.
- The timing of the interim visits between Week 16 and Week 48 will depend on the patient's injection regimen, i.e. q12w or q8w.
- No visits are planned between the injection visits.
- The last potential study treatment may be administered at the Week 40 visit or at the Week 44 visit according to the patient's treatment regimen.
- A disease activity assessment will also be performed at the Week 48/EOS visit; however, no study treatment will be administered.

The different types of visits occurring through the study are summarized in [Table 6-3](#) with a description of when disease activity assessment and treatment take place.

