## Unscheduled visits

If a patient returns to the site prior to his/her next scheduled study visit, the investigator will capture the unscheduled visit in the eCRF only in the case of a clinically significant abnormal finding.

If this finding leads to an AE and/or the decision to treat the patient prior to his/her next scheduled treatment, all the procedures listed for the Interim Visit need to be conducted and captured in the eCRF.

In the case of a treatment decision for nAMD treatment is made during the unscheduled visit (at the exception of AE treatment), the assigned study medication can not be administrated. In case of administration of an anti-VEGF medication during an unscheduled visit, it will be considered as the use of a prohibited treatment and should be managed as described in [Section 9.1.1](#).

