## 9 Study discontinuation and completion

### 9.1 Discontinuation

#### 9.1.1 Discontinuation of study treatment

Discontinuation of study treatment for a patient occurs when study treatment is stopped earlier than the protocol planned duration, and can be initiated by either the patient or the investigator.

The investigator must discontinue study treatment for a given patient if he/she believes that continuation would negatively impact the patient's well-being.

The investigator and/or referring physician will recommend the appropriate follow-up medical care, if needed, for all patients who are prematurely withdrawn from the study.

Study treatment must be discontinued under the following circumstances:

- Patient requires treatment on a q4w interval after the initiation phase, i.e., after the three monthly injections at Baseline, Week 4, and Week 8, followed by the first interval extension
- Patient develops intraocular inflammation, including retinal vasculitis and/or retinal vascular occlusion
- Patient/guardian decision
- Pregnancy
- Use of prohibited treatment
- Any situation in which study participation might result in a safety risk to the patient

If premature discontinuation of study treatment occurs, the following should be done as appropriate:

- The investigator should make a reasonable effort to understand and document the primary reason for the patient's premature discontinuation of study treatment using the appropriate eCRF page.
- Patients who prematurely discontinue study treatment for any reason should return 4 weeks after last study treatment to perform the assessments for early treatment discontinuation (ETD). Please refer to [Table 8-1](#), except for patients who withdraw their consent from the study and do not wish to do so (refer to [Section 9.1.2](#)).
- After these assessments are performed, patient can be switched to standard of care (SOC) anti-VEGF IVT as per investigators discretion. IVT injection is contraindicated in patients with active intraocular or periocular infections and in patients with active intraocular inflammation; therefore, the investigators must verify that these conditions are not present in the study eye prior to every injection.
- After premature study treatment discontinuation, at a minimum till week 48, in abbreviated visits, the following data should be collected at clinic visits or via telephone/email contact:
  - New/concomitant treatments

- Adverse events/Serious Adverse Events
- BCVA

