### 12.5 Analysis of secondary endpoints

#### 12.5.1 Efficacy endpoints

All secondary efficacy analyses will be based on the FAS. The analyses performed at eye level will focus on the study eye only.

The secondary efficacy endpoints are as follows:

- Functional outcomes of brolocizumab
  - Change in BCVA from Baseline up to Week 48.
- Anatomical outcomes of brolocizumab
  - Percentage change in CNV lesion area measured by OCT-A from Baseline to Week 48.
  - Change in OCT-A features assessed by qualitative and quantitative criteria from Baseline by visit at Week 12 up to Week 48.
  - Change in SD-OCT features assessed by qualitative and quantitative criteria (e.g. CSFT, sub- and/or intraretinal fluid, sub-RPE fluid) from Baseline by visit at Week 12 up to Week 48.

The continuous functional and anatomical outcomes will be analyzed using the same primary method of analysis as the primary efficacy analysis. The factors in the respective model will be defined by the study Steering Committee. These details will be provided in the SAP. The qualitative dichotomous anatomical outcomes with 2 categories will be assessed using Cochran's Q Test and those with more than 2 categories by the Generalized McNemar's Test. In addition, the functional and anatomical outcomes will be described descriptively.

- Dosing regimen of brolocizumab
  - Proportion of patients who are maintained on an exclusive q12w interval following the loading phase through Week 48.
  - The probability of the first q12w interval for determining successful q12w maintenance at Week 48.
  - Time from last IVT injection in the initiation phase to first visit with no disease activity

The binomial proportion and 95% confidence interval (CI) using the Clopper-Pearson method will be provided for disease status (i.e. q12w treatment status) at each disease activity assessment visit. The estimate of the probability for a patient to be maintained on the q12w regimen up to end of treatment will be summarized based on a Kaplan-Meier analysis of time to first q8w need. The time from last IVT injection in the initiation phase to first visit with no disease activity will also be summarized using a Kaplan-Meier analysis. In addition, descriptive statistics will also be provided.

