Change from Baseline: The difference of measure between post-baseline and Baseline is called change from Baseline.

Percent change from Baseline: The percent change from Baseline will be calculated as below: ((post-baseline value – Baseline value) /Baseline value)*100.

On-treatment period: The on-treatment period lasts from the date of first administration of study treatment to 28 days after the date of the last actual administration of any study treatment.

Treatment duration: The maximum planned duration of treatment for each patient is 40 to 44 weeks in accordance with the designated treatment regimen. Discontinuation of study treatment for a patient occurs when study treatment is stopped earlier than the protocol planned duration and can be initiated by either the patient or the investigator.

Treatment discontinuation: When patients discontinue study treatment but continue in the study, the efficacy data will be used at the time the patient stopped study treatment.

Dry retina: Absence of fluid (IRF/SRF/sub-RPE) will be considered as dry retina.

Event for maintenance q12w interval: In case the investigator selects q12w interval for a patient and the patient maintains the q12w interval until the first q8w interval has started then this will be considered as an event. In case the investigator maintains q12w interval (does not select q8w interval at any time in study) until EOS or patients got early discontinuation from study then patients will be considered as censored.

Event for no disease activity: When patients will be with no disease status as per investigator decision after last dose in initiation phase then the patients will consider as event for disease activity. If patients with active disease status or early discontinue then patients will be considered as censored for disease activity.

Event for dry retina: When patients have absence of fluid then it will be considered as an event of dry retina. If patients have a presence of fluid before/at EOS or early discontinuation then will be censored.

Maximum duration of dry retina: The longest consecutive interval of dryness will be considered as maximum duration of dryness. This duration will be obtained from end date of dryness and start date of dryness for longest interval. If subjects obtain dryness at end of study then duration will be obtained from end of treatment.

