2.6.1.5 Dosing regimen of brolucizumab

The binomial proportion and 95% CI using the Clopper-Pearson method will be provided for patients who are maintained on an exclusive q12w interval following the loading phase through Week 48.

The number and percentage of q8w dose frequency patients will be presented along with 95% CI using the Clopper-Pearson method.

Duration of dose is defined as (date of last dose – start date of dose).

The summary statistics (n, mean, std, first quartile, median, third quartile, min and max) for duration of dose will be provided for patients who are maintained on an exclusive q12w interval following the loading phase through Week 48. In the study design the 3×4 -week dosing frequency, in initiation phase.

The above analysis will be done only on the study eye. The analysis will be performed on the FAS.

2.6.1.5.1 Predictive value of the first q12w cycle for maintenance of q12w treatment with brolucizumab

The probability of the first q12w interval will be derived from KM time to event analyses. KM plot will be provided. Detailed KM results will be presented including time (week), number of patients under risk at visit, number of patients with first q12w or discontinue at visit, probability of maintaining on q12w (survival probability) and 95% CI for maintaining on q12w.

Variable	Definition	
Start date	First date when patients on q12w interval	
Event	Fail maintain to q12w interval	
End date	Last date of initial q12w interval (before or on first start of q8w interval)	
Censoring (end date)	Completed/Discontinue with q12w	
Duration of time	(End date – start date) +1	

The above analysis will be done only on the study eye. The analysis will be performed on FAS.

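### The Kaplan-Meier analysis of q12w maintenance censors patients who stop study treatment directly from q12w because they needed treatment sooner, which biases the q12w probability upward

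*SAP*

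**What the plan says.** Protocol 12.5.1 takes the probability of staying on q12w from a "Kaplan-Meier analysis of time to first q8w need".

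SAP Addendum 1.0, section 2.1.1, makes the start of the first q8w interval the event. A patient for whom q8w is never chosen is censored at end of study. Of those who leave early it says: "patients got early discontinuation from study then patients will be considered as censored". Section 2.6.1.5.1 relabels the event as a failure to maintain q12w, but still dates it only by the first q8w interval. Its censoring row is "Completed/Discontinue with q12w", with no split by reason. The separate Clopper-Pearson proportion in 2.6.1.5 concerns "patients who are maintained on an exclusive q12w interval following the loading phase through Week 48", on the FAS, with no explicit sentence about early stoppers.

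The protocol gives three routes off study treatment that do not pass through q8w:

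- Section 6.7.2 states: "No visits are planned between the injection visits". If nAMD treatment is decided at an unscheduled visit, study drug may not be given, and Section 8 adds: "In case of administration of an anti-VEGF medication during an unscheduled visit, it will be considered as the use of a prohibited treatment". Under 9.1.1 that ends study treatment.
- Section 6.2.3 provides no rescue. "In case of lack of efficacy with the investigational drug for nAMD", an investigator who wants a prohibited treatment for the patient follows the stopping instructions.
- Section 9.1.1 requires a stop when "Patient requires treatment on a q4w interval after the initiation phase".

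Unless they withdraw consent, these patients are to remain in the study (6.1.4).

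**The concern.** A patient who could not wait 12 weeks has failed q12w, whether or not the investigator recorded a q8w interval first. Under the SAP such a patient enters the Kaplan-Meier analysis as a censored observation. The method then treats the patient as having the same future chance of staying on q12w as those still on it. That assumption fails here, because the reason for leaving is the outcome itself. The bias goes one way: the q12w probability comes out too high.

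The rule also sits oddly beside the missed-visit rule (protocol 6.7.2, repeated in SAP 2.1.1). A patient who merely misses Week 20 or Week 32 is assumed active and moved to q8w, and so becomes an event. A patient with a demonstrated need for earlier treatment may not.

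At stake are two named secondary endpoints, the proportion kept on q12w and the predictive value of the first q12w cycle.

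**Working it through.** **Step 1. Follow patients who are on q12w through both documents.**

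| Patient on q12w | Protocol consequence | SAP Kaplan-Meier status | 12 weeks too long? |
|---|---|---|---|
| Active at Week 16, 20, 32 or 44 | Moved to q8w | Event | Yes |
| Misses Week 20 or 32 | Assumed active, moved to q8w | Event | Assumed |
| Other anti-VEGF at an unscheduled visit | Prohibited treatment, stops | Censored | Yes |
| Lack of efficacy, prohibited treatment wanted | Stops | Censored | Yes |
| Needs q4w before any q8w interval | Stops | Censored | Yes |
| Intraocular inflammation | Stops | Censored | Not shown |
| No activity to the end | Completes | Censored | No |

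Rows three to five are the gap. No analysis set removes the anti-VEGF patients either: SAP Table 5-1 keeps prohibited medication in every set.

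**Step 2. Inputs.** The plan states no expected q12w figure. Its only planned number is the sample size, which reproduces: (1.96 × 35 / 5)² = 188.2, so 189; 189 / 0.90 = 210. I take 210 as the FAS.

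The rest is assumed, because the documents give no rates. Protocol 4.5 says that fewer than half of patients in the pivotal trials had activity after loading, and that most interval adjustments came in the first q12w interval. In line with that:

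- 72 patients go to q8w in the first cycle, 10 at Week 32 and 8 at Week 44 (90/210 = 42.9%).
- k patients stop directly from q12w after the first cycle, with k = 4 (about 2%) or 11 (about 5%), split between Weeks 20-32 and 32-44 as 2 + 2 or 6 + 5.

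**Step 3. Kaplan-Meier estimate at Week 48**, the product of (1 − events / at risk), started at the first q12w date as 2.6.1.5.1 specifies. The first-cycle factor is 1 − 72/210 = 138/210.

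k = 4: at risk 138 − 2 = 136 at Week 32 and 136 − 10 − 2 = 124 at Week 44.
- Censored (SAP): (138/210)(1 − 10/136)(1 − 8/124) = 57.0%
- Counted as failures: (210 − 72 − 10 − 8 − 4)/210 = 116/210 = 55.2%
- Difference 1.7 points (from unrounded values)

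k = 11: at risk 138 − 6 = 132 and 132 − 10 − 5 = 117.
- Censored (SAP): (138/210)(1 − 10/132)(1 − 8/117) = 56.6%
- Counted as failures: 109/210 = 51.9%
- Difference 4.7 points

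**Step 4. A different pattern as a check.** Assume 92 switches (50, 25, 12 and 5 at Weeks 16, 20, 32 and 44), with half of the direct stops before Week 20.
- 4 stops: (1 − 50/210)(1 − 25/158)(1 − 12/132)(1 − 5/119) = 55.9%, against 114/210 = 54.3%; difference 1.6.
- 10 stops: (1 − 50/210)(1 − 25/155)(1 − 12/128)(1 − 5/113) = 55.3%, against 108/210 = 51.4%; difference 3.9.

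Direction and rough size agree.

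**Step 5. The proportion.** Each stopper moves it by 1/210 = 0.5 points. With k = 11, counting stoppers as not maintained gives 109/210 = 51.9% (95% CI 44.9 to 58.8). Counting them as maintained gives 120/210 = 57.1% (50.2 to 63.9).

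**The case against.** The routes are narrow. A q12w patient found active at a scheduled visit goes to q8w and is already an event. The q4w clause in 9.1.1 applies only after the first interval extension, so many such patients will already have been on q8w. What remains is mainly treatment at unscheduled visits and lack-of-efficacy stops, and the documents give no frequency for either. This stands, and it limits the size of the problem.

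The protocol itself turns need into a visit decision: activity seen, patient reassigned to q8w. That is fair for patients seen at scheduled visits. It does not cover those who leave between visits or need 4-weekly dosing, whose need exceeds q8w.

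The Addendum could be read as already curing this. It relabels the event as failure, and one output column in 2.6.1.5.1 pools discontinuations with a count by regimen. But that column is unclear, and the event date and censoring row say the opposite. Protocol 12.4.3, which sits under the primary endpoint, censors efficacy data when treatment stops. Applied here, it would discard the very event that caused the stop.

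The 2.1.1 sentence speaks of leaving the study, whereas these patients stop treatment and stay. The result does not change: they are censored at end of study under 2.1.1 or at the stop under 2.6.1.5.1, and in neither case are they events.

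For the proportion, the objection largely succeeds. Exclusive q12w through Week 48 on the FAS naturally makes an early stopper not maintained. A reader might infer from the 2.1.1 definition that stoppers count as successes, but that text defines a Kaplan-Meier event, not a binomial response.

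Finally, these are descriptive secondary endpoints in a single-arm study without a hypothesis test. That is true, and it sets the priority of the point. It does not remove the bias.

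**Conclusion.** The point holds for the Kaplan-Meier analysis. As written, the SAP censors direct stops from q12w made because treatment was needed sooner, and so overstates q12w maintenance relative to the protocol's definition. Under the assumed 4 to 11 such stops in 210 patients, the excess is about 1.7 to 4.7 points. That is less than the 95% CI half-width of about 6.9 points for a proportion near 57%, but always in the favourable direction. The stop counts and the timing of q8w switches are assumptions; only their general shape comes from protocol 4.5. For the proportion, one clarifying sentence is enough.

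Three stronger readings are not supported:

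- *A larger error in the predictive value.* Restricting the Step 3 scenario to the 138 who pass the first cycle gives 86.7% against 84.1%, and 86.1% against 79.0%, or 2.6 to 7.1 points. The SAP analysis starts at the first q12w date and does not condition on passing that cycle.
- *The 10% allowance (21 patients) as a bound on stops.* It covers drop-out and uninterpretable images at Baseline and Week 12, not treatment stops to Week 48.
- *The inflammation rates of 3.2% and 5.3% as the number affected.* These are rates in men and women for all inflammation-related events. Such stops do not show that 12 weeks was too long, and censoring them remains appropriate.

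The Week 12 primary endpoint and the sample size are unaffected.

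**What to change.** In SAP 2.1.1 and 2.6.1.5.1, define the event as the earliest of (a) the start of the first q8w interval and (b) study treatment stopped for q4w need, lack of efficacy, or other anti-VEGF in the study eye. Censor all other stops at the date study treatment stopped. Standard-of-care anti-VEGF begun after a stop for another reason, such as inflammation, is not an event. Date type (b) events by the decision to stop, because the SAP's treatment end date is the last injection and would place the failure at the start of the interval. Align the output column with this definition.

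In 2.6.1.5, state that FAS patients who stop study treatment early are not maintained on q12w through Week 48, and report early stops by reason beside the proportion.

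The cost is a few SAP sentences and one derived flag. SAP 2.3.1 already lists lack of efficacy, new therapy for the indication and prohibited treatment as reasons. It has no code for q4w need, so those cases must be found by review, for example under lack of efficacy or physician decision. Prohibited treatment must be split, since protocol Table 6-2 also covers items other than anti-VEGF. The drawbacks are that the q12w figures may be slightly lower, and that the event will depend partly on a reason recorded by an open-label investigator.

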## **Post-treatment follow-up period: from Week 40/44 to Week 48**

For all patients completing the study as per protocol, the End of Study (EOS) assessment will be performed at Week 48, 4 weeks (for patients treated at Week 44) or 8 weeks (for patients treated at Week 40) ( $\pm 7$  days) following their last possible study treatment administration.

Patients withdrawn from the study prior to study completion will be asked to return for an EOS/Early Discontinuation Visit, 4 weeks ( $\pm 7$  days) following their last study treatment administration. For early treatment discontinuations (ETD) refer to [Section 9.1.1](#).

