**Table 8-1 Assessment schedule for the study eye**

Period	Treatment Period							Follow-up	
	Initiation Phase			q12w/q8w Phase				EOS  ETD 	M 
Visit	Screening/Baseline 					Interim Visits 	EOT‡		
	Day 1	Week 4	Week 8	Week 12	Week 16	Every 8 or 12 weeks according to treatment regimen	Week 40/ Week 44	Week 48	
Informed consent	X								
Inclusion/exclusion criteria	X								
Demography	X								
Medical history/current medical conditions	X								
Vital signs	X	X	X	X	X	X	X	X	
Prior/concomitant medications (including surgery and procedures)	X	X	X	X	X	X	X	X	X
Adverse events	X	X	X	X	X	X	X	X	X
BCVA score (ETDRS)	X	X	X	X	X	X	X	X	X
IOP	X							X	
Ophthalmic examination and imaging 	X	X	X	X	X	X	X	X	
SD-OCT 	X	X	X	X	X	X	X	X	
OCT-A 	X	X	X	X	X	X	X	X	
CFP 	X			X				X	
FAF	X			X				X	
FA 	X 			X					
ICG 	X			X					
Disease activity assessment	X	X	X	X	X	X	X	X	
Study drug IVT injection 	X	X	X		X 	X 	X 		
Telephone follow-up post injection 	X after 1st injection								

Note: Mandatory study visits are highlighted in grey.

Abbreviations: BCVA=best-corrected visual acuity, CFP=color fundus photography, EOS=end of study, ETDRS=early treatment diabetic retinopathy study, FA=fluorescein angiography, FAF=fundus autofluorescence, ICG=indocyanine green chorioangiography, IVT=intravitreal, OCT=optical coherence tomography

‡ The end of treatment will occur at either Week 40 or Week 44 according to the treatment schedule.

 The Screening/Baseline visit are performed on the same Visit.

 The number of weeks between visits will vary depending on the disease stability and length of intervals between injections as determined by disease activity assessment.

 Include slit lamp examination and fundus examination

 If FA has been made as required by the protocol during the 15 days prior to screening, FA does not need to be repeated on Screening/Baseline visit. In this case, FA image needs to be collected and reviewed by the CRC.

 ICG is optional at the discretion of the investigator. ICG should be performed at week 12 if it has been performed at Screening/Baseline.

 Treatment according to investigator decision based on disease activity assessment.

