2.1.1 General definitions

Study treatment: This is a single-arm study and all patients will be treated with brolucizumab 6 mg. Three loading injections (at Screening/Baseline/Day 1, Week 4 and Week 8), followed by maintenance treatment from Week 16/Week 20 up to Week 40/Week 44. The investigator can individualize treatment intervals depending on disease activity, to adjust patient's injection regimen.

Study treatment start and end date: Study treatment start date is defined as the first date study treatment is administered and recorded on the treatment administration record (DAR) electronic case report form (eCRF) page. Similarly, study treatment end date is defined as the last date of study treatment is administered and recorded on the study treatment completion CRF page.

Generally, study day 1 is considered as the day of inclusion of the patient. However in this study, treatment is intended to be administered on the same day or if this is not possible, within 3 days after the day of inclusion of the patient.

Study day will be calculated as (event date – study treatment start date + 1 day) for events that occurred on or after study treatment start date (e.g. visit, AEs). For events prior to study treatment start date (e.g. time since diagnosis), study day will be negative and calculated as (event date – study treatment start date).

Baseline and post-baseline: Baseline value refers to the value of the last non-missing measurement collected prior to administration of the first dose of study treatment (Screening or Baseline visit). Intraocular pressure (IOP) will be assessed in the study eye, pre-dose and post-dose at every injection. The last available assessment taken prior to the first IVT injection of study treatment is taken as the "Baseline" assessment.

A "post-baseline" value refers to a measurement taken after the first dose of study treatment. When assessments and treatments take place on the same day, treatment must occur after completion of the efficacy assessments and pre-injection safety measures (tonometry, slit lamp and fundus examinations). If study visit assessments and the corresponding treatment occur on separate days, a repeat safety check-up will be performed prior to treatment of the eye and

results documented in the source documents. More post-baseline safety measurements will be recorded in source document; visit window will be applied to OCT and IVT visits.

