2.6.1.2.5 Maximum duration of dryness

The median of maximum duration of dryness until Week 48/50 will be presented. The median will be obtained from the KM analysis along with 2-sided 95% CI. KM plot will be provided.

Detailed KM results will be presented including time (week), total number of patients having fluids (risk), number of patients under achieved maximum duration (event), probability of maximum duration of dryness (survival probability) and 95% CI.

Variable	Definition	
Start date	Start date of treatment	
Event	Dryness	
End date of event	Start date of dryness	
Censoring (end date)	Earliest of:	
	Absence of dryness until EOS	

		Early discontinuation with absence of dryness
Duration of	time	(End date – start date) +1 (Maximum duration will be used)

The above analysis will be done only on the study eye. The analysis will be performed on FAS.

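### The SAP's end-of-treatment rule for eyes dry at study end is ambiguous, no reading gives the longest dry interval for all eyes, and the derivation table contradicts it

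*SAP*

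**What the plan says.** Addendum 1.0 added a definition of maximum duration of dry retina to SAP section 2.1.1. It has three sentences.

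- The concept: "The longest consecutive interval of dryness will be considered as maximum duration of dryness".
- The dates: "This duration will be obtained from end date of dryness and start date of dryness for longest interval".
- A special rule: "If subjects obtain dryness at end of study then duration will be obtained from end of treatment".

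End of treatment has a meaning elsewhere in the documents. In the same SAP section, "study treatment end date is defined as the last date of study treatment is administered". The footnote to protocol Table 8-1 says "The end of treatment will occur at either Week 40 or Week 44 according to the treatment schedule". The end-of-study visit, which includes an SD-OCT, is at Week 48.

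The analysis itself is in SAP section 2.6.1.2.5: "The median of maximum duration of dryness until Week 48/50 will be presented". The median is to come from a Kaplan-Meier analysis on the FAS. The derivation table there starts the clock at treatment start, ends it at the start of dryness, and censors eyes that have not become dry by end of study or by early discontinuation. It contains no end-of-treatment term.

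**The concern.** The date of the last injection neither starts nor ends a dry run. It falls before the last scheduled SD-OCT, so using it either discards dryness seen at Week 48 or counts dryness from a date unrelated to when the eye became dry. The sentence leaves two things open: whether end of treatment is the start or the end of the interval, and whether the rule covers every eye dry at Week 48 or only eyes that first become dry then.

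An eye still dry at its last scan has an ongoing dry run, which a duration analysis would normally treat as right-censored. Section 2.1.1 gives no censoring rule for this quantity, and the table in 2.6.1.2.5 censors the opposite group, the eyes that never became dry. Two programmers could follow the SAP faithfully and report different medians.

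**Working it through.** **Inputs**

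- Scheduled days (SAP Table 2-1): Week 12 = 84, Week 40 = 280, Week 44 = 308, Week 48 = 336.
- Duration formula (SAP 2.6.1.2.5): end date minus start date, plus 1.
- End of treatment = last injection, planned at Week 40 or Week 44.

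**The plan's own figure.** Protocol section 3 puts end of study at "4 weeks (for patients treated at Week 44) or 8 weeks (for patients treated at Week 40") after the last possible injection. From the scheduled days, 336 - 308 = 28 days (4 weeks) and 336 - 280 = 56 days (8 weeks). It reproduces.

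**Reference values**, with the interval closed at the Week 48 scan:

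- Eye dry from Week 12 through Week 48: 336 - 84 + 1 = 253 days.
- Eye first dry at Week 48: 336 - 336 + 1 = 1 day.

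**Reading A: end of treatment is the end date.**

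- Dry from Week 12: 308 - 84 + 1 = 225 days, or 280 - 84 + 1 = 197 days. The loss is 28/253 = 11% or 56/253 = 22%.
- First dry at Week 48: 308 - 336 + 1 = -27 days, or 280 - 336 + 1 = -55 days. Neither is a valid survival time.

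**Reading B: end of treatment is the start date for every eye dry at end of study.**

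- Both eyes get 336 - 308 + 1 = 29 days, or 336 - 280 + 1 = 57 days.
- For the eye dry from Week 12 the loss is (253 - 29)/253 = 89% or (253 - 57)/253 = 77%.

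**Reading C: the rule covers only eyes first dry at Week 48, counted from end of treatment.**

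- Those eyes get 29 or 57 days instead of 1, although they were not dry at the Week 44 or Week 40 scan.
- The eye dry from Week 12 keeps 253 days.

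**The 2.6.1.2.5 table as written**, with treatment start on Day 1:

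- Dry from Week 12: 84 - 1 + 1 = 84 days.
- First dry at Week 48: 336 - 1 + 1 = 336 days.

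This is time to first dryness. A longer value means a later response, the reverse of a duration of dryness.

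| Rule | Dry Week 12 to 48 | First dry at Week 48 |
|---|---|---|
| Closed at Week 48 scan | 253 | 1 |
| A (last injection Week 44 / Week 40) | 225 / 197 | -27 / -55 |
| B (Week 44 / Week 40) | 29 / 57 | 29 / 57 |
| C (Week 44 / Week 40) | 253 | 29 / 57 |
| 2.6.1.2.5 table | 84 | 336 |

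**Range of the gap.** With both visits at opposite limits of the ±7-day window, the Week 44 gap runs from (336 - 7) - (308 + 7) = 14 to (336 + 7) - (308 - 7) = 42 days. The Week 40 gap runs from (336 - 7) - (280 + 7) = 42 to (336 + 7) - (280 - 7) = 70 days. A missed last injection or an early stop gives other gaps.

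**The case against.** Four objections have weight.

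- **The harm depends on the reading.** A reader might infer that the rule always gives a negative time to an eye first dry at Week 48, or that it both shortens and replaces long dry intervals. The documents do not support that. Negative times arise only under reading A, and shortening (A) and replacement (B) are alternatives.
- **The verb allows a narrow rule.** To obtain dryness at end of study can mean to become dry for the first time then. Under that reading C, eyes dry since Week 12 are untouched, so it cannot be said that the best responders are necessarily the ones distorted. This stands, but C still credits 29 or 57 days to an eye with a single dry scan.
- **The table may be what is programmed.** If so, none of the figures under A to C arises. That does not clear the sentence. The table then fails to measure duration of dryness at all, and the SAP holds two incompatible derivations under one name.
- **Importance is limited.** Maximum duration of dryness is not named in protocol Table 2-1. It is an SD-OCT summary set out in the SAP.

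A reader might also infer that the rule biases a comparison of q8w with q12w. No dryness comparison by regimen is planned, and the week of last injection does not cleanly mark regimen: a switch to q8w at Week 20 leads to injections at Weeks 20, 28, 36 and 44, the same last week as q12w.

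**Conclusion.** The point holds as a defect of specification. Every reading of the sentence gives some eyes a duration that is not their longest dry interval, and the choice of reading alone moves one patient by up to 253 - 29 = 224 days. The sentence conflicts with the definition that precedes it and with the stated scope up to Week 48/50. The 2.6.1.2.5 table follows neither.

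The figures rest on nominal visit days and on patients treated to plan. How many eyes are affected cannot be derived from the documents, because it depends on the reading and on how many eyes are dry at Week 48. What is at risk is a supportive Kaplan-Meier median. The primary endpoint, percentage change in CNV lesion area at Week 12, is not touched. The SAP should be corrected, but the trial's main conclusion does not depend on it.

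**What to change.** Make two changes together, because either one alone leaves a contradiction.

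1. **Section 2.1.1.** Delete the end-of-treatment sentence. State instead that the interval runs from the first dry SD-OCT of the longest dry run to the end of that run, and is censored at the last SD-OCT (Week 48/end of study, or early discontinuation) if the eye is still dry.
2. **Table in 2.6.1.2.5.** Start = start of the dry run; event = end of dryness; censored = still dry at end of study or at early discontinuation. SAP Amendment 2.0 already had these start and end dates and this censoring, though it labelled the event as dryness, so the label should change too.

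With these rules the two example eyes get 253 days and 1 day, both censored, and no negative times arise. The SAP should also say how eyes that never become dry are reported, since they have no dry interval. The cost is one replaced sentence, one revised table and the matching programming change. No new data are needed.
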